did not own a phone had access to one supporting the feasibility of using mobile phones as a medium for health interventions.³²

Feasibility Study Results

From June 2017 to January 2018, YP Action conducted a feasibility study of an online support group intervention designed to improve ART adherence and health service retention among YLHIV (FHI 360 PHSC study number 930307). The feasibility study included a pilot test of 5 structured sessions delivered by trained facilitators through Facebook groups to groups of 8 YLHIV. A total of 41 participants completed a baseline questionnaire; 38 of 41 enrolled and participated in the online groups. For those who did not participate, one was excluded because her literacy was determined to be too low to effectively participate after recruitment, one person fell ill and was unable to participate in the initial group meeting so was excluded, and a third person dropped out because she said there was no cellular network coverage near her home. Thirty-five of 38 participants completed the endline interview.

All 35 respondents reported at endline that they: enjoyed being a member of the online group; received useful information from the group; better understood their HIV infection after participating in the group; and felt comfortable interacting with both the other members and the facilitators. All 35 respondents also agreed that they would like to continue to be part of the group, that Facebook groups are a good way for young people with HIV to interact and that such groups are a good way to get information to people living with HIV.

Among the 35 participants who completed the endline interview, 34 reported participating in at least one online session, with the 35th person reporting connectivity issues. About half (n=16) participated in all five sessions and 26 participated in three or more sessions. In terms of posting frequency, which was daily, five people stated they felt the facilitator postings were too frequent, and 27 reported the frequency was about right. Thirty-one out of 35 reported that they made new friends through the group.

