Each SMART Connections group will consist of approximately 15 to 20 YLHIV, and approximately 15 groups in total will be formed. Once a sufficient number of YLHIV have been recruited and randomized to form a group, the group will begin with an initial, in-person group meeting with the group facilitator. Online groups will be formed by local government area to ensure participants are able to travel to this initial meeting.

During this meeting, the participants will have an opportunity to meet one another, possibly for the first time, and the facilitators face-to-face. The intent and design of the intervention will be described and ground rules for participation will be set. Ground rules will be discussed and accepted by the group members, but at a minimum, group members will be advised not to talk about what is discussed in the online group with people outside of the group. A brief activity that highlights confidentiality and the consequences of breaking confidentiality will be implemented. During this meeting, the participants will also receive their study phones and the facilitator will record their contact information (telephone numbers, email addresses and Facebook ID). Those who prefer can use their existing sim card (in the study phone), phone or Facebook ID to participate in the project, as long as they are willing to provide the information to the facilitator to enable them to be enrolled in the group. The facilitator will enroll each participant into the virtual group, and then a demonstration of how to open, log-in, post comments and log-out of the group will be made. Each participant should demonstrate the ability to log in and out to the facilitator. The facilitator will also set conditions and expectations for responding to posts and messages by the facilitator, such as limiting his/her responses to group members to business hours and perhaps certain times of the day. Also, the facilitator will instruct the participants if they need to contact the facilitator individually, to send a message to call back when it is safe to do so without risk of breaking confidentiality and the facilitator will call the person.

For those participants who are randomized to the control arm, they will receive their study phone when they return for their next clinic visit.

Standard of care services

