The primary population of interest for this study is YLHIV, ages 15-24 years in Akwa Ibom and Cross River, Nigeria. Eligibility criteria to participate in the study include:

- HIV positive and know their status
- Actively on ART for up to 12 months including newly initiating patients
- Age 15 to 24 years
- Can demonstrate basic literacy necessary to participate in online chats³

Exclusion criteria include:

- Unable to attend the initial intervention group meeting for treatment participants
- Currently enrolled in another research study related to HIV service retention or ART adherence
- Critically or severely ill requiring hospitalization or such that the individual is unable to provide informed consent at the time of study recruitment

Sample Size and Sampling Design

Sample size

Our primary outcome is retention in HIV care. We will need to recruit 250 experimental participants and 250 control participants to be able to detect a 0.125 difference in the cumulative probability of retention at 12-months (0.45 in the control group and 0.575 in the intervention group), corresponding to a hazard ratio of 0.69, with 80% power and 5% significance level for a two-sided comparison using the log-rank test. These calculations also assumed exponential times to event and a 10% loss to follow-up.

Sampling procedure and recruitment: Eligible participants will be sequentially recruited from patients who attend clinic visits at the study facility until the total sample size has been achieved. Patients currently attend ART clinic visits monthly. If recruitment extends beyond 8 weeks, alternately, we will ask the health ART clinic point person to identify potentially eligible patients based on eligibility criteria from their facility records and to contact the person by telephone to tell them about the study and, if interested, to invite them to come to the facility if they may be interested in participating in a research study.

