		LGA Facility Est. # of eligible patients per facility		Total	% of	Distribution of sample by study arm				
State	LGA			per LGA	sampl e	Control Arm (n=250)	Treatment arm (n=250)			
		Ikot Ekpene Primary Health Centre	70	130	17.69	4.4	4.4			
	Ikot Ekpene	Ikot Ekpene General Hospital	60		%	44	44			
	Mbo	Enwang Primary Health Centre	20	87	10.88	27	27			
		Okobo General Hospital	12		7.070/	1.0	1.0			
Akwa	Okobo	Okopedi Primary Health Centre	40	52	7.07%	18	18			
Ibom	Oron	Oron General Hospital (Iquita)	65	146	19.86	50	50			
	Oron	Oron Operational Base PHC	81	140	%	30	30			
		Idu-Uruan Primary Health Centre	34		15.10					
	Uruan	Ituk Mbang Methodist General Hospital	77	111	%	38	38			
	Uyo	Uyo Base Primary Health Centre	88	1177	15.92	40	40			
	Оуо	University of Uyo Teaching Hospital	29	11//	%	40	40			
	Calabar Municipal	Calabar General Hospital	39							
Cross River	Calabar South	[name] Memorial Hospital	20	39 60	13.47 %	34	34			
		Ekpo Abasi Primary Health Center	40							
			Totals	735	100%	250	250			

Randomization procedures

A randomization manager from FHI 360, who is not otherwise involved in the study, will prepare a computerized randomization list using permuted blocks before the start of the study. These envelopes will be given to study staff in charge of the enrollment process. These staff will open the randomization envelopes and inform the participant which group s/he has been assigned to. Participants will be randomized in a 1:1 ratio to proceed with the study procedures. The master randomization list will be maintained at FHI 360 and will not be available to study staff.

Randomization groups will be concealed in sequentially numbered, sealed opaque envelopes (SNOSE). We will instruct study staff never to open an envelope until the participant has given consent to participate in the study, is found to be eligible for the study, and is available to start intervention and control study procedures. The opened randomization envelopes will be retained as source documents and will be kept under secure and restricted access to protect the confidentiality of the participants.

This is an open-label study – neither study staff nor participants will be blinded to study treatment arms after the point of randomization. Nonetheless, strict policies will be in place to preserve randomization integrity. Randomization documentation will be stored in a secure location. Data recording, assessment of

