the primary and secondary study outcomes, and other assessments will be blinded to treatment arm where possible.

In-depth Interviews

Participants

IDIs will be conducted at the conclusion of the intervention sessions with a sub-set up to 36 purposely selected YLHIV participants (who are 18 years of age and older) assigned to the intervention group from in the original sample at the conclusion of the SMART Connection sessions. The sample will include up to 12 individuals per group who are classified as:

- Having moderate/high participation in the group
- Having low participation in the group
- Having opted not to join the group to which they were assigned

Participants in the on-line support groups will be categorized as having moderate/high participation or low participation, based on the assessment of the online support group facilitators based on participants' frequency of posts, likes, comments on posts, and private messages to the facilitator. Those who are categorized as moderate/high participation will be asked questions to explore their perspective (likes, dislikes and suggestions for improvement) on the intervention platform, intervention content, and the implementation of the three components (push informational messages, moderated group chats and unstructured access to peers and their counselor through the Facebook site). For those with low participation, we will explore reasons for non-participation and suggestions for changes, if any that could serve to enhance participation. We will also conduct IDIs with participants who were randomized to the intervention arm but did not join an online support group to explore reasons for non-participation and experiences with the study outcomes independently from the intervention. Within each of these three participant groups, we will purposely sample participants who have good retention in care and those who have not been retained in care or who have missed some clinic appointments.

Data collection

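### An exclusion criterion worded for the intervention arm depends on a meeting held after randomisation, and the plan does not say that non-attenders stay in follow-up and analysis

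*Protocol*

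**What the plan says.** - **Protocol, Study Population, exclusion criteria:** "Unable to attend the initial intervention group meeting for treatment participants".
- **Protocol, Intervention Description (timing):** "Once a sufficient number of YLHIV have been recruited and randomized to form a group, the group will begin" with an in-person meeting. Groups hold about 15 to 20 youth and are formed by local government area (LGA).
- **Same section, control arm:** no meeting; "they will receive their study phone when they return for their next clinic visit".
- **Protocol, Randomization procedures (repeated in SAP III):** staff are told "never to open an envelope until the participant has given consent to participate in the study, is found to be eligible for the study", and the participant must also be available to start the procedures of both arms.
- **Protocol, In-depth Interviews, Participants:** interviews are planned with "participants who were randomized to the intervention arm but did not join an online support group".
- **Protocol, Feasibility Study Results:** of 41 enrolled at baseline, "one person fell ill and was unable to participate in the initial group meeting so was excluded".
- **SAP IV, General Analytic Considerations:** primary analyses follow intention-to-treat, with participants analysed as randomised whatever errors or violations occur. The protocol's own Analyses section states no such rule.
- **SAP VI, Objective 1:** the Kaplan-Meier listing and plot are grouped by `group_itt`, but the log-rank command uses `group`. Under Objective 2 the SAP labels `group` as treatment exposure.

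**The concern.** Eligibility should be settled on information available before allocation and in the same way for both arms. As worded, this criterion names one arm and refers to an event that is scheduled only after allocation. When the envelope is opened, the meeting may have no date.

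Someone applying the list literally could declare an intervention participant ineligible after randomisation because that person was ill, away at school or already drifting out of care. The same person in the control arm would stay in. Ability to come to an in-person meeting is plausibly related to the primary outcome, which is coming to the clinic, although the documents give no data on that link. If the link exists, one-sided removal raises apparent retention in the intervention arm with no true effect. If follow-up of those removed also stopped, the analysis could not repair it.

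The passages that protect against this (the check before allocation, intention-to-treat, interviews with non-joiners) are not reconciled with the criterion. Nothing states what happens to a randomised youth who then meets it.

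**Working it through.** **1. The plan's own figure.** Inputs from Sample size (Protocol; repeated in SAP III): 12-month retention 0.45 and 0.575, 250 per arm, 80% power, two-sided 5%, exponential times, 10% loss.

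- Hazard ratio = ln(0.575)/ln(0.45) = 0.693 (plan: 0.69).
- Schoenfeld events = 4(1.960 + 0.842)²/(ln 0.693)² = 234.
- With exponential loss of 10% over the year, rate g = -ln(0.9), the event probability for event rate λ is p(λ) = λ/(λ+g) × (1 - e^-(λ+g)). This gives 0.526 and 0.405, mean 0.4655.
- N = 234/0.4655 = 503, against 500 planned. Power at 500 is 79.9%.

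The sample size reproduces and is not in dispute.

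**2. Effect of one-sided removal when there is no true effect.** Let f be the share of the intervention arm removed and r the 12-month retention of those removed. Neither is given for this trial. The pilot offers f = 1/41 = 2.4%, about 6 of 250. The values of r are assumptions: 0 (all lost, the worst case), 0.225 (half the average) and 0.45 (average).

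- Apparent intervention retention S1 = (0.45 - f·r)/(1 - f).
- Apparent HR = ln(S1)/ln(0.45).
- Events D = 250·p(control) + 250(1 - f)·p(S1).
- Drift μ = √(D·a(1 - a)) × |ln HR|, where a is the intervention share of those analysed.
- Two-sided rejection = Φ(μ - 1.96) + Φ(-μ - 1.96).

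For f = 1/41 and r = 0:

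- S1 = 0.45/0.9756 = 0.461; HR = 0.969.
- D = 250 × 0.526 + 243.9 × 0.515 = 257; μ = 0.25.
- Rejection = 0.044 + 0.013 = 5.7%.

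| Removed f | Retention of removed r | S1 | Spurious gain | HR | Type I error |
|---|---|---|---|---|---|
| 1/41 | 0.225 | 0.456 | 0.6 points | 0.98 | 5.2% |
| 1/41 | 0 | 0.461 | 1.1 points | 0.97 | 5.7% |
| 10% (assumed) | 0.225 | 0.475 | 2.5 points | 0.93 | 8.5% |
| 10% (assumed) | 0 | 0.500 | 5.0 points | 0.87 | 19.4% |
| any | 0.45 | 0.450 | 0 | 1.00 | 5.0% |

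A log-rank simulation (4,000 runs) of the 10%, r = 0.225 case gave 8.7%. For scale, the design difference is 12.5 points.

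**3. With everyone kept as randomised.** In the same simulations, across 5% to 20% hard-to-reach youth, type I error was 4.6% to 5.5%, which is nominal within simulation error. N stays at 500.

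**The case against.** The opposing case is substantial.

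- **The wording can be parsed differently.** The last words of the criterion may describe the meeting, not limit who is screened. Candidates are assessed before enrolment, and anyone can say in advance whether they could travel to a meeting in their LGA. This is a fair reading, but the text does not say so, and a meeting with no date yet cannot be fully settled in advance on either reading.
- **There is an availability check before allocation.** The envelope stays shut until the candidate "is found to be eligible for the study, and is available to start intervention and control study procedures". This is close to the proposed remedy and covers both arms. Forming groups by LGA and reimbursing travel also help. None of it says what happens when someone judged available does not come.
- **A reader might infer that non-attenders leave the analysis.** No passage says so. The SAP's intention-to-treat rule, the interviews with non-joiners, exposure defined by assignment in the measures tables, and outcomes taken from clinic records all point the other way. This stands, and it is why the point is an unreconciled conflict and not a shown bias. The security is incomplete because the rule does not name this case and the log-rank command uses `group`.
- **A reader might infer that the pilot already did this.** It excluded one person for missing the meeting, but its description mentions no randomisation or control arm, so it shows no differential removal.
- **A reader might take the pilot's 3 of 41 non-participants as the rate,** giving about 12% type I error if all were lost. Only one of the three concerns this criterion. The others were low literacy, now screened for beforehand, and lack of network coverage.

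**Conclusion.** The point holds as a defect of wording and an unresolved conflict between passages. The criterion is worded for one arm, rests on a meeting held after randomisation, and has no counterpart for controls. Applied literally, it permits removal from the intervention arm alone.

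At the only rate in the documents that concerns this criterion, 1 of 41, the spurious gain is at most about 1.1 points and the type I error about 5.2% to 5.7%. The 8.5% to 19.4% range assumes 10% removed, which no document supports. The pilot rate may be low for this trial: the pilot took youth at least 6 months on ART, this trial admits new initiators, and the protocol reports the greatest losses early in treatment. That is a reason for care, not a removal rate.

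Bias requires three things together: the literal reading, removal despite intention-to-treat, and below-average retention in those removed. With average retention there is none. The figures use the 12-month design values, not the SAP's 270-day analysis with a 28-day cutoff. A reader might conclude that randomisation is broken; the documents do not support that. Severity: should fix, not must fix.

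**What to change.** 1. **Protocol, Study Population.** Reword the criterion so that it is put to every candidate before the envelope is opened, for example: *Unable or unwilling to attend an in-person group meeting in their LGA if assigned to one.*
2. **Protocol, Study Population and Randomization procedures, and SAP IV.** State that, once a participant is randomised, failure to attend the meeting or join a group is not an exclusion, and that the participant stays in follow-up and in `group_itt` with outcomes abstracted from clinic records.
3. **SAP VI, Objective 1.** Use `group_itt` in the log-rank command, as the Kaplan-Meier commands already do.
4. **If enrolment is complete.** This is likely, since the protocol's timeline places enrolment in 2018 and the SAP is dated December 2019. Make changes 2 and 3, and restore anyone removed under this criterion.

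Cost: one reworded criterion, one screening question, one sentence repeated in three places and one variable name. A few candidates who would have been controls are screened out. Clinic records are abstracted anyway, so keeping non-attenders adds almost nothing, and sample size and power do not change.

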Participants will be asked to respond to structured questionnaires through face-to-face interviews conducted by trained interviewers using computer tablets prior to the launch of the intervention, after completing the intervention sessions and at the end of the study period. Data to be collected include: basic demographic information (e.g. sex, age, education level, relationship status (e.g. married, partnered, single), living arrangements (whether they live with a parent or guardian, how many people are in their household, and relationship to those people), as well as contact information (phone number, place of residence); HIVrelated information including how long since diagnosis, current ART regimen, last CD4 and viral load test date and results, disclosure status, self-reported adherence; social support measures covering emotional, instrumental, informational and network social support dimensions; factors associated with poor retention and adherence, including depression/anxiety, alcohol and other substance use, and perceived and experienced stigma; and access to and use of mobile telephones and social media applications. Forms will be administered at baseline and again at six months and endline, which will be 6 and 12 months after the intervention is initiated, respectively. Six-month and endline questionnaires will include additional, closedand open-ended questions pertaining to intervention participation. Telephone interviews may be conducted in place of face-to-face interviews for participants who, after at least 2 attempts to schedule in-person interviews, are unable or unwilling to return to the clinic for interviews after the intervention and at the end of the study period.

Clinical data

A data abstraction sheet will be developed to abstract relevant clinical data for each study participant. Trained data collectors will abstract data periodically (approximately quarterly) through 15 months after enrollment. As noted, the form will only record the participant's unique study ID for identification purposes. Data to be abstracted will include: date and results of CD4 cell counts and viral load tests; date of HIV diagnosis; date of ART initiation; WHO clinical stage at ART initiation; dates of ART refills; dates of ART clinic visits.

Participation data

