Randomization groups will be concealed in sequentially numbered, sealed opaque envelopes (SNOSE). We will instruct study staff never to open an envelope until the participant has given consent to participate in the study, is found to be eligible for the study, and is available to start intervention and control study procedures. The opened randomization envelopes will be retained as source documents and will be kept under secure and restricted access to protect the confidentiality of the participants.

This is an open-label study – neither study staff nor participants will be blinded to study treatment arms after the point of randomization. Nonetheless, strict policies will be in place to preserve randomization integrity. Randomization documentation will be stored in a secure location. Data recording, assessment of the primary and secondary study outcomes, and other assessments will be blinded to treatment arm where possible.

IV. General Analytic Considerations

All primary analyses will be conducted under the intent-to-treat (ITT) principle, whereby participant data will be analyzed in the group each participant is randomized to regardless of randomization errors or other protocol violations. A per protocol analysis will be conducted if more than 5% of the population is affected by protocol violations such as randomization errors.

A. Data Sources

1. Structured questionnaires

Topics: Demographic information; HIV-related information; social support measures;

depression/anxiety, alcohol and other substance use, and perceived and experienced stigma; and access to and use of mobile telephones and social media applications. Sixmonth and endline questionnaires will include additional questions pertaining to intervention participation.

Timing: Baseline, endline

Source: Structured interview

Format: Face-to-face interview with data entered on a mobile tablet Population: Intervention participants

2. Clinical data abstraction

Topics: Date and results of CD4 cell counts and viral load tests; date of HIV diagnosis; date of ART initiation; WHO clinical stage at ART initiation; regimen substitutions and switches;

treatment discontinuation and interruptions; dates of ART refills; dates of ART clinic visits. Timing: Periodically, through 12 months after enrollment.

Source: Electronic medical record system at participating health clinics Format: Electronic form captured on mobile tablet

Population: Intervention participants

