- ltfu 90=0; retained ٠ o v2 ltfu 90==0 AND v3 ltfu 90==0 AND v4 ltfu 90==0, etc. AND the earliest value of today el, today el approx, latest mre falls within 90 days of latest instance of **vnq044**
- ltfu 90=8; transferred out ٠
 - o Retained up to the date of transfer (transfer==1 and q027, transfer date, must be non-missing)
 - **ltfu 90**=9; died o Retained up to the date of death (death==1 and q028, death date, must be non-missing)

ret time 28 Time in days retained until LTFU, transfer, death, or censor

- If 1tfu 28=0
 - o ret time 28==[latest follow-up date i.e. v8q044] [BL survey date, today bl] IF v8q044<today el/today el approx</pre>
 - o ret time 28=[latest visit date i.e. v7q036]+28-today bl IF retained for all visits recorded and latest available follow-up date is missing
 - o ret time 28=[today el/today el approx]-today bl IF latest follow-up date >today el/today el approx OR latest visit date +28 >today el/today el approx
- If **1tfu 28**=1
 - o ret time 28=[latest follow-up date prior to LTFU, i.e. v6q044] -[today bl]
 - o ret_time_28=latest visit date prior to LTFU, i.e. v5q036 + 28 today bl IF latest follow-up date prior to LTFU is missing
- if **1tfu 28**=8
 - o ret time 28=latest follow-up date prior to or after transfertoday bl IF q027>today bl AND q027≤latest follow-up date prior to transfer
 - o ret time 28=latest visit date prior to transfer + 28 -today bl IF q027>today bl AND latest follow-up date prior to transfer is missing
- if **1tfu 28=9**
 - o ret_time_28=q028-today_bl

ret time 90 Time in days retained until LTFU, transfer, death, or censor

- If **ltfu 90=0**
 - o ret_time_90==[latest follow-up date i.e. v8q044] [BL survey date, today_b1] IF v8q044<today el/today el approx</pre>
 - o ret_time_90=[latest visit date i.e. v7q036]+28-today_b1 IF retained
 for all visits recorded and latest available follow-up date is
 missing
 - o ret_time_90=[today_el/today_el_approx]-today_bl IF latest follow-up
 date >today_el/today_el_approx OR latest visit date +28
 >today_el/today_el_approx
- If **ltfu_90**=1
 - o ret_time_90=[latest follow-up date prior to LTFU, i.e. v6q044] [today_b1]
 - o ret_time_90=latest visit date prior to LTFU, i.e. v5q036 + 28 today_bl IF latest follow-up date prior to LTFU is missing
- if **ltfu_90**=8
 - o ret_time_90=latest follow-up date prior to or after transfertoday_bl IF q027>today_bl AND q027≤latest follow-up date prior to transfer
 - o ret_time_90=latest visit date prior to transfer + 28 -today_bl IF

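### The envelope may be opened before the baseline interview, yet the SAP starts the retention clock at that interview and not at randomisation

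*Protocol*

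**What the plan says.** **Opening the envelope.** Protocol, Randomization procedures, sets three conditions. Staff are "never to open an envelope until the participant has given consent to participate in the study, is found to be eligible for the study", and until the person "is available to start intervention and control study procedures". SAP section III repeats the rule: "is found to be eligible for the study, and is available to start intervention and control study procedures". Neither list names the baseline questionnaire. The enrolment staff open the envelope and tell the participant the result, and from then on neither is blinded. Blinded assessment is promised only as far as it is possible.

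**Timing of the baseline interview.** Protocol, Structured questionnaires, places the interviews "using computer tablets prior to the launch of the intervention, after completing the intervention sessions and at the end of the study period". Launch is the only limit on the first of them.

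**Timing of launch.** Protocol, Intervention Description: "Once a sufficient number of YLHIV have been recruited and randomized to form a group, the group will begin" with a face-to-face meeting. Launch therefore comes after randomisation. The control arm has no launch; controls collect their phone at their next clinic visit.

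**The retention clock.** SAP section IV.C, Retention for survival analysis, computes ret_time_28 and ret_time_90 by subtracting the "BL survey date, today bl" in every branch. The SAP hypothesis itself is timed from enrolment.

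**The concern.** Two things follow from an unstated order.

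First, social support, knowledge, adherence, stigma and depression are self-reported to an interviewer. If those answers can be given after both people know the arm, they are no longer guaranteed to be independent of allocation. The social-support and knowledge tests subtract them.

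Second, the time origin of the primary analysis becomes an event that can fall after allocation, and whose occurrence and timing could depend on it. The SAP commits to intention to treat, but its survival variable exists only for people who have a baseline interview date.

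**Working it through.** No figure in the plan is in dispute here, and the sample-size calculation is not involved. The check is to set the passages side by side.

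**Step 1: is baseline after allocation compliant?** The envelope needs consent, eligibility and availability. The interview must come before launch. Launch comes "Once a sufficient number of YLHIV have been recruited and randomized to form a group". In the intervention arm, an interview held between envelope opening and the first group meeting breaks no stated rule. In the control arm no upper limit is stated. The Protocol timeline puts enrolment and baseline collection in one row and does not order them against randomisation.

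**Step 2: what does the clock measure?** Write R for the randomisation date, B for the baseline survey date (today_bl), E for the date at which retention ends or is censored, and δ = B − R.

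- SAP time = E − B = (E − R) − δ.
- *B missing.* E − B cannot be computed. The SAP's missingness rules cover a missing follow-up date, death date or transfer date, records that stop early, and no visit data at all. None covers a missing today_bl. The primary analysis is complete-case, and the imputation planned under Objective 1 excludes retention itself, so such a participant drops out.
- *B later than R.* Day 270 on the SAP clock is day 270 + δ from randomisation. The arms' windows differ by δ(intervention) − δ(control), which is zero if the delays are equal.
- *B later than E.* The time is negative. The SAP's origin of −0.01 is explained as keeping participants with zero survival time; negative times are not addressed. With monthly visits this needs a baseline later than a scheduled visit date, so it would take a long delay.

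**Step 3: does the SAP treat enrolment and baseline as the same day?** Not entirely. It defines visit 1 as the first visit attended after enrolment, and its code for n_visits then handles a visit 1 dated before today_bl. The code thus allows the two dates to differ. It does not show how often they do, or in which arm.

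**Step 4: where do baseline answers enter the results?**

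| Analysis | Use of baseline self-report |
|---|---|
| Retention status (primary) | None; taken from medical-record dates |
| Social support and knowledge t-tests | Subtracted as change scores |
| Adherence and viral suppression chi-square tests | None; endline only |
| Regression models for Objective 2 | Covariates such as baseline depression, isolation, hunger and adherence |
| Mediation (Objective 3) | Change in social support |

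For the primary outcome the exposure is therefore through the date of the interview. For social support and knowledge it is through the answers.

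**The case against.** The strongest reply is that baseline was almost certainly done at enrolment. Enrolment and baseline share one timeline row. Rescheduling and telephone fallbacks are written for the six-month and endline interviews but not for baseline. Travel is reimbursed for the interviews and the group meeting, with no separate randomisation visit. In the feasibility study 41 people completed baseline and 38 went on to the groups. The third envelope condition can also be read as assuming that enrolment steps are finished. All of this is fair and makes a long gap less likely. None of it is a rule, and the SAP code in Step 3 shows that the dates were not assumed to coincide.

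Three stronger readings are tempting, and the documents do not support them.

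- *That baseline interviews were in fact done after allocation.* The text permits this and says no more.
- *That the number of losses before the clock starts can be calculated from the sample-size hazard.* Loss is dated at a missed scheduled visit, visits are typically monthly, and most participants are recruited at a visit they attend. For such a person no loss can be dated in the first weeks, so a continuous hazard from day 0 does not describe this endpoint.
- *That the change scores are biased by some stated amount.* Neither document gives a basis for how far knowing the arm would move an answer.

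It also stands that equal delay in both arms does not by itself bias the comparison, and that changing the envelope rule probably comes too late. The timeline shows enrolment in September to November 2018, while the Protocol version is dated March 2019 and the SAP December 2019.

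**Conclusion.** The point holds as a defect in the stated time origin and as an unstated order of baseline and allocation. It does not establish bias.

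Certain from the text: baseline after envelope opening is permitted; ret_time_28 and ret_time_90 start at the baseline survey date; and no rule covers a randomised participant who lacks that date.

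Not known: how many such participants there are, how long δ is, and whether it differs by arm. The size of any effect is therefore unknown. It is zero for the clock if every baseline was done on the day of randomisation. An equal delay in both arms leaves no between-arm shift of the origin, although participants without a baseline date would still be lost from the analysis.

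A correction is still warranted because the trial is open-label, the primary analysis is declared intention to treat, and the randomisation date is an origin that does not depend on an interview.

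**What to change.** 1. Count ret_time_28 and ret_time_90 from the randomisation date. Keep every randomised participant with record data in the intention-to-treat survival analysis, with or without a baseline interview. The approximate endline date and the 56-day record-completeness flag also use the baseline date and should move with it.
2. Report by arm the interval from randomisation to baseline, the number of baseline interviews dated after randomisation, and the number of participants with no baseline.
3. If any baseline came after randomisation, add a sensitivity analysis of the social-support and knowledge change scores without those participants.
4. If enrolment is still open, add to the envelope conditions in both documents *and has completed the baseline questionnaire*, and change the limit in Protocol, Structured questionnaires, to *before randomisation*.

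The cost is a change of origin date in the code and one table. The opened envelopes are kept as source documents, so they are the place to look for the date if it is not already in the data set; the documents do not say whether it was written on them. No visit is added. If all baselines were done on the day of randomisation, the results do not change and the table shows why.
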